17.1 Primary Efficacy Endpoint: mean SOFA score d2-d5

Summary and statistical analysis of the primary endpoint will be done using the FAS and the PPS.

The primary analysis compares the average post-baseline patient SOFA score (average over days 2-5). The average post-baseline score will be compared between both groups with a two-sided test derived from a constrained longitudinal data analysis (cLDA) model using a likelihood approach with alpha equal to 0.05 and a Kenward-Roger approximation of the denominator degrees of

freedom. Rules to handle missing SOFA scores are discussed in section 10. The choice of the covariance structure for the five measurements in the cLDA model will be based on the Aikake criterion. Site will be added as a fixed factor in the model. The cLDA analysis is valid under the missing at random assumption (MAR) and assumes that the probability that an observation is missing depends only on observed values of the individual, but not on the missing ones. An inverse hyperbolic sign transformation will be applied to handle the (right-)skewed distribution of the SOFA scores. Results will be presented after back-transformation to the original scale. As such, the estimate for the treatment effect will refer to a ratio instead of to a difference. Results on untransformed SOFA scores will be reported as sensitivity analyses.

17.2 Secondary Efficacy Endpoints

Summaries and statistical analyses of the secondary endpoints will be done using the Full Analysis Set and the Per Protocol Set.

17.2.1 Length of hospital stay

To evaluate differences in length of hospital stay, death during hospital (ICU) stay will be treated as a competing risk (Brock et al. 2011), using a stratified Gray's test for the comparison of both groups. Patients not yet discharged will be censored.

17.2.2 Length of ICU stay

The same approach as for length of hospital stay will be used. The analysis will be restricted to patients admitted in ICU. Note however that the time starts at the moment of ICU admission and not at the moment of randomisation (this to handle the possibility that patients need to go the ICU at a later moment during the follow-up).

17.2.3 SOFA score at d2-d5

From the cLDA model used for the primary endpoint, mean values at d2, d3, d4 and d5 will be compared with two-sided tests and 95% confidence intervals will be reported.

17.2.4 Maximal SOFA score during d2-d5

The maximal SOFA score will be compared using a two-sided unpaired t-test after inverse hyperbolic sign transformation. For patients who are discharged, the observed maximum SOFA will be used. If there are patients with a missing SOFA score due to administrative reasons, a multiple imputation approach (20 imputed datasets) will be considered since the observed maximum can be underestimated for these patients. Multivariate imputation will be performed for the daily SOFA scores using the fully conditional specification (FCS) approach (Van Buuren et al., 2007), separately in each treatment arm. For the imputation, linear models will be specified for each daily SOFA score (ordered d5-d1) with as regressors the SOFA scores on the other days. The seed value will be set at 15112023.

17.2.5 28-day mortality

28-day mortality will be compared using a stratified χ^2 test (study site as stratum). 95% confidence intervals will be reported for the percentage mortality in each treatment group and for the odds ratio. However, when there are subjects lost to follow-up before 28 days, 28-day estimates will be

derived from the Kaplan-Meier curve and compared using a Z-test (on the complementary log-log scale).

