The required sample size is calculated to detect with at least 80% power a difference in average post-baseline patient SOFA score (calculated over days 2 to 5), based on a constrained longitudinal data analysis model with alpha set at 0.05 (Liang and Zeger, 2000). The power is calculated using an approach presented by Stroup (Stroup, 1999). In the cLDA, both the baseline and post-baseline value are modeled as dependent variables, as opposed to a (longitudinal) ANCOVA model in which the baseline value is included as a covariate. Although the baseline measure is included in the response vector in cLDA, the true baseline means are constrained to be the same for different treatment groups due to randomization, and this analysis provides an adjustment for the observed baseline difference in estimating the treatment effects. Since the randomization is performed within center, considering center as an effect in the analysis has no impact on the sample size. Patients who die within the time period of 5 days receive the worst outcome (highest SOFA score) starting at the day of death. Based on the cLDA model, 126 patients per group (252 patients in total) are needed to detect with at least 80% power a difference between the control and intervention group of 1 in average post- baseline SOFA score. A standard deviation of the SOFA score equal to 3.5 and a correlation between the time points equal to 0.5 was assumed. These were conservative estimates, derived from reported information in two studies (Fowler et al, 2019; Fujii et al. 2020). 2.5%, 5%, 10% and 15% missing values are assumed on d2, d3, d4 and d5, respectively (combination of dropout and mortality). However, the sample size will be increased to 150 patients per group to anticipate a larger variability due to the imputation of one or more maximal SOFA scores for deceased patients.

7 Analysis Populations

The following analysis sets will be of interest:

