8.3 Centre Effect

All statistical analyses of the outcomes of interest will be adjusted for study site. When applying the adjustment, the small site ULB Erasme (3 patients in the FAS) will be combined with UZ Brussels (Jette), as decided during the Blind review meeting (September 25, 2023).

9 Methods for Missing Data

In the statistical analyses of the longitudinally measured outcomes the presence of missing values is handled using a direct likelihood approach to fit the multivariate models. As such, the analysis is valid under the missing at random assumption (MAR).

Handling missing data for the SOFA score

In some settings, the following rules for single imputation will be used to handle missing SOFA scores or missing components for the calculation of the SOFA score.

- Patients who die within the time period of 5 days receive the worst outcome (highest SOFA score being equal to 24) starting at the day of death (even if a SOFA score is available at the day of death).
- SOFA scores are considered missing after the day of discharge
- If the patient's status does not require a lab analysis (due to good condition of the patient), missing data occur as per protocol. In this case the best possible score will be used for the SOFA score calculation (i.e. 0 points for bilirubin, blood platelets and creatinin) in the daily follow-up.
- If however a lab analysis was not ordered but was required as per protocol, the SOFA score of that day will be considered as missing.
- If a lab analysis was required, but one of the three lab values needed in the SOFA score was missing, the previous lab value was used for the calculation of the SOFA score. This was deemed appropriate, since it can be assumed that the specific lab parameter was not ordered that day because the function was considered stable. In rare cases where this happened at d1, the value of d2 will be used for the calculation of the SOFA score.

Frequency tables will be reported for the various settings where above imputation rules were applied.

For the analysis of the maximal SOFA score a multiple imputation approach will be used (cfr infra for details of the imputation model).

10 Data Transformations

An inverse hyperbolic sign transformation will be applied in the analysis of the (maximal) SOFA to obtain a more symmetric distribution of the model residuals. Analyses on untransformed scores will be reported as sensitivity analyses.

11 Multicenter Study

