All analyses will be adjusted for study site if feasible. No adjustment will be considered for binary outcomes (or time-to-event outcomes) when a low number of events yields computational problems.

12 Stratification Factors

Randomization was stratified for study site. Therefore, all models that are used for the estimation of treatment effects will be adjusted for study site.

13 Multiple Comparisons

Since only 1 primary endpoint is defined, no adjustment of the significance level is required.

For secondary efficacy endpoints, due to the exploratory nature of the efficacy analyses, no adjustment for multiple comparisons will be made.

14 Planned Subgroups, Interactions and Covariates

Moderator analyses will be performed for the primary outcome.

It will be verified if the treatment effect depends on the following baseline variables:

- baseline SOFA
- baseline NEWS score

For the baseline SOFA score, subgroups will be defined (<6 vs ≥ 6). Appropriate summary statistics per treatment arm and estimated treatment effects will be presented for each subgroup. In addition, the interaction between the above subgroups and treatment effect will be tested to assess whether the treatment effect differs according to subgroup.

The baseline NEWS score will be evaluated as a continuous moderator by including the main effect of the baseline NEWS score and the interaction between the baseline NEWS score and the treatment effect in the analysis model, allowing non-linearity for the relation of the baseline NEWS score (using restricted cubic splines with 4 knots).

Subgroup analyses will only be performed for the FAS.

15 Disposition of Study Subjects

A summary by treatment group will be provided for the following:

- Number of randomized subjects,
- Number treated according to randomization
- Number in Full Analysis Set (FAS)
- Number in Per Protocol Set (PPS)
- Exclusions from FAS
- Exclusions from PPS
- Number of subjects who died in hospital up to Day 5
- Number of subjects who were discharged up to Day 5

16 Demographics and Other Baseline Characteristics

All data recorded at baseline will be summarized by treatment group. Since it is a randomised study, no statistical tests will be performed to compare these data between the groups.

Summaries will be presented for FAS and PPS separately.

The following baseline information will be presented:

- Age, (y)
- Sex
- Weight (kg)
- NEWS score at ED presentation

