17.2.9 Dose and need of steroids

The daily dose of steroids given will be compared between both groups using a multivariate normal model for longitudinal measurements, with the Aikake criterion to select the covariance matrix. The mean dosage over d2-d5 will be compared, as well as the timepoint specific dosages. Study site will be added in the model. Note that the model will be fit on information from all patients in the period d1-d5. For discharged, lost-to-FU and deceased patients, the dose will be put on missing.

The need of steroids (MV) will be compared using a generalised linear mixed model (i.e. a logistic regression model with a random effect of patient) with site added as a fixed effect. An odds ratio will be reported for the comparison of the 'mean probability' over d2-d5, and for the day-specific comparisons.

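### Maximal SOFA is tested with an unpaired t-test that has no place for study site, although the plan requires all analyses to be adjusted for site

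*SAP*

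**What the plan says.** Maximal SOFA over days 2 to 5 is a listed secondary outcome (SAP 4.2.2). Its analysis is fixed in 17.2.4: "The maximal SOFA score will be compared using a two-sided unpaired t-test after inverse hyperbolic sign transformation". If scores are missing for administrative reasons, 20 imputed datasets are considered, imputed by arm from the SOFA scores on the other days. Site enters neither the test nor the imputation.

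The general rule on site appears three times:

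- Section 8.3: "All statistical analyses of the outcomes of interest will be adjusted for study site". The same section pools a three-patient site with another site for this purpose.
- Section 11 repeats the rule for all analyses where feasible and adds one specific exception: "No adjustment will be considered for binary outcomes (or time-to-event outcomes) when a low number of events yields computational problems".
- Section 12 gives the reason, stratified randomisation, and concludes that "all models that are used for the estimation of treatment effects will be adjusted for study site".

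The primary SOFA analysis in 17.1 follows the rule: "Site will be added as a fixed factor in the model". Steroid dose (17.2.9), fluid balance (17.2.10) and EQ-5D-5L (17.2.11) each carry the instruction "Study site will be added in the model".

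**The concern.** The plan gives two instructions for one endpoint, and they are incompatible. Two analysts who each follow the SAP could report different standard errors and p-values for maximal SOFA.

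There is also a statistical consequence. Stratified randomisation balances the arms within site, so differences between sites contribute little to the true variance of the treatment contrast. The t-test still counts those differences as residual noise. Its standard error is therefore too large, and the test is slightly conservative and slightly underpowered.

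Two further points have less weight:

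- **Day 1 SOFA.** The t-test ignores it. Section 6 says of the cLDA that "this analysis provides an adjustment for the observed baseline difference in estimating the treatment effects", so the other SOFA endpoints gain this precision and maximal SOFA does not. This breaks no stated rule.
- **28-day mortality (17.2.5).** Any loss to follow-up before day 28 replaces the site-stratified test by estimates "derived from the Kaplan-Meier curve and compared using a Z-test", with no mention of site. That trigger is not the sparse-events exception of Section 11.

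**Working it through.** **1. Does any exception apply?** The plan gives no figure to reproduce here, so the passages are compared directly.

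- The Section 11 exception needs a binary or time-to-event outcome and few events. Maximal SOFA is analysed as continuous, so it does not apply.
- The feasibility proviso in Section 11 does not help. The primary cLDA fits site as a fixed factor to the same daily scores, and the smallest site is already pooled. A site term for one value per patient is easier to fit.
- Every other continuous endpoint with a described model has a site term: 17.1, 17.2.3 (through the cLDA), 17.2.9, 17.2.10 and 17.2.11.
- Sections 17.2.7 and 17.2.8 do not mention site, but they name regression models that can take it under the general rule. The t-test cannot.

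**2. Size of the site effect.** Inputs from the SAP are two-sided alpha 0.05 (Section 17) and 300 patients allocated 1:1 (Section 3). The share of outcome variance due to site, here called ICC, is not given and is assumed to lie between 0.01 and 0.15.

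- SE inflation = 1/√(1 − ICC)
- Actual type I error = 2 × [1 − Φ(1.96/√(1 − ICC))]
- Power of the t-test where the adjusted model has 80% = 1 − Φ(1.96/√(1 − ICC) − 2.80), with 2.80 = 1.96 + 0.84

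| Assumed ICC | SE inflation | Type I error | Power of t-test |
|---|---|---|---|
| 0.01 | 1.005 | 0.049 | 79.7% |
| 0.05 | 1.026 | 0.044 | 78.5% |
| 0.10 | 1.054 | 0.039 | 76.9% |
| 0.15 | 1.085 | 0.034 | 75.0% |

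Simulation check A used about 300 patients, 5, 8 or 10 equal sites balanced within site, and 40,000 trials per setting. At ICC 0.01, 0.05 and 0.10 the t-test's type I error was 0.047–0.050, 0.044–0.046 and 0.039–0.040. The site-adjusted test stayed at 0.048–0.051.

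Simulation check B used 300 patients, 8 unequal sites, permuted blocks of 4 and 6,000 runs per setting. At 5%, 10% and 15% the t-test's type I error was 0.044, 0.040 and 0.038, against 0.050–0.054 with site adjustment. The t-test lost 1.3, 3.0 and 4.0 points of power.

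**3. Possible gain from day 1 SOFA.** SD 3.5 and correlation 0.5 come from Section 6. The following are assumed: compound symmetry, scores rounded and limited to 0–24, baseline mean 5 to 8, 0–8% deaths by day 5 scored 24, and 0–40% discharged before day 5 with the observed maximum used. There were 105 scenarios of 300,000 patients each.

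- Correlation r of transformed day 1 SOFA with transformed maximum: 0.386–0.544 if death and discharge are unrelated to baseline, and up to 0.553 if related.
- Variance reduction r²: 0.149–0.296, and up to 0.306.
- SE reduction 1 − √(1 − r²): 0.078–0.167.
- Equivalent extra patients 1/(1 − r²) − 1: 0.175–0.441, or about 18–44%.

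**4. How often the mortality fallback is used.** With 300 patients and independent losses, P(at least one loss) = 1 − (1 − loss rate)³⁰⁰. Assumed loss rates of 0.5%, 1% and 2% give 0.778, 0.951 and 0.998. This shows how often the fallback would apply, not how much harm it does.

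**The case against.** The strongest reply is that the site rule is stated three times, with the pooling already fixed, so a reader would let it govern and treat 17.2.4 as loose wording. The endpoint is exploratory with no multiplicity control (Section 13), the error is conservative, and every size above rests on an ICC that the SAP does not give. All of this is fair, and it limits the priority. It does not remove the conflict: if the general rule governs, the test named in 17.2.4 is the wrong one and the text must still change.

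A second reply is that the day 1 SOFA figures are the largest here but concern an optional gain. That stands. Section 6 describes baseline adjustment as a property of the cLDA, not as a duty for every SOFA endpoint, so those figures do not measure the contradiction.

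A third reply is that 17.2.5 is only silent on site. A Kaplan-Meier comparison can be combined over strata, and feasibility within sites is a real question for deaths. That also stands, so the mortality point is a request for clarification and not a second contradiction.

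**Conclusion.** The concern holds. Section 17.2.4 names a test that cannot comply with Sections 8.3, 11 and 12, and neither the sparse-events exception nor the feasibility proviso excuses it. For an assumed site ICC of 0.01 to 0.10 the standard error is 0.5% to 5.4% too large, and power falls by 0.3 to 3.1 points from 80%. The treatment estimate is not biased and false positives do not increase. Leaving out day 1 SOFA costs precision only, and type I error stays nominal. The correction should be made because the conflict is clear and the remedy nearly free. Priority is modest.

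**What to change.** In 17.2.4, replace the t-test by a linear model of transformed maximal SOFA with treatment and site as fixed factors, using the site pooling of Section 8.3. This alone resolves the contradiction. Adding transformed day 1 SOFA as a covariate is recommended for precision. Where imputation is used, include site in the imputation models and combine the estimates over the 20 datasets. If the t-test is to be kept, the SAP should state that this endpoint is exempt from the site rule and why.

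In 17.2.5, state that site is kept in the fallback comparison where feasible and dropped only under the Section 11 exception. Pseudo-value regression with site is one option.

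The cost is SAP wording and one model statement for maximal SOFA, plus a sentence in 17.2.5. No new data are needed and the sample size does not change.

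### Maximal SOFA (SAP 17.2.4): unless deceased patients are kept out of the imputation models, their 24s push imputed maxima of survivors upward; a minor bias with a nearly free fix

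*SAP*

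**What the plan says.** SAP 17.2.4 compares the maximal SOFA score over days 2 to 5 by an unpaired t-test after an inverse hyperbolic sine (asinh) transformation. Discharged patients are not imputed: "For patients who are discharged, the observed maximum SOFA will be used". Imputation is reserved for administratively missing scores; for those, the section says that "a multiple imputation approach (20 imputed datasets) will be considered since the observed maximum can be underestimated for these patients".

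The imputation is run "separately in each treatment arm", and "linear models will be specified for each daily SOFA score (ordered d5-d1) with as regressors the SOFA scores on the other days". The section names the transformation for the t-test only. For the imputation it gives no scale, bounds or rounding, and it does not say whether deceased patients belong to the data on which the models are fitted.

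Section 9 (Methods for Missing Data) lays down that those who die within the five days "receive the worst outcome (highest SOFA score being equal to 24) starting at the day of death". Addendum 1 codes the same rule. Section 17.1 describes the SOFA distribution as right-skewed.

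**The concern.** The 24 of a deceased patient is an assigned worst value, often far from that patient's own scores on earlier days. In a linear model that predicts one day from the others, such jumps become large residuals. The model has one residual variance, so the draws for survivors with a missing day inherit the extra spread.

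For a mean, symmetric extra noise would roughly cancel. For a maximum it does not: a high draw replaces the observed maximum, and a low draw changes nothing. Because each arm has its own models, the inflation follows that arm's deaths. If deaths differ, the arm with more deaths gets the larger upward shift among its survivors, in addition to the 24s it carries legitimately.

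The section's own reason for imputing is that the observed maximum may be too low. A procedure that overshoots partly defeats that purpose.

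**Working it through.** The SAP states no figure for this imputation, so there is none to reproduce. It gives no death rate by day 5, no share of administratively missing days and no early-death difference between arms. The only anchor, in section 6, is 2.5%, 5%, 10% and 15% missing on days 2 to 5 for dropout and mortality combined, an average of (2.5 + 5 + 10 + 15)/4 = 8.1%. Those quantities are therefore assumed and varied.

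**1. Mechanism.** Suppose the observed maximum is m and one missing day is drawn from a normal distribution with mean μ and SD σ. The expected rise of the maximum is σ[φ(z) − z(1 − Φ(z))], with z = (m − μ)/σ. In simulation B below, at correlation 0.5, the residual SD rises from about 2.8 with no deaths to about 3.6 with 10% deaths.
- m = μ: 0.399 × 2.8 = 1.12 and 0.399 × 3.6 = 1.44, a difference of 0.32 points.
- m − μ = 2: 0.39 and 0.65, a difference of 0.26 points.

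The wider residual SD alone thus adds roughly 0.3 points per imputed patient in this example.

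**2. Simulation B.** 150 per arm; right-skewed SOFA with mean 5 and SD 3.5; 24 from the day of death; arm-specific linear models ordered d5 to d1; 20 imputations; 2% or 5% of patient-days administratively missing (about 6–17% of patients affected); correlation 0.5 or 0.8; 40 replicates per setting. Error of the maximum in affected patients, in raw points (simulation noise roughly 0.1):

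| Deaths by day 5 | Models including the 24s | Models on survivors only |
|---|---|---|
| none | −0.06 to +0.15 | – |
| about 3% | +0.12 to +0.23 | +0.02 to +0.16 |
| about 6% | +0.25 to +0.33 | +0.05 to +0.11 |
| about 10–11% | +0.36 to +0.59 | +0.01 to +0.10 |

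Without imputation the maximum in the same patients is too low by 0.3 to 0.8 points.

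On the tested asinh scale, the error per affected patient is the arm-mean bias divided by the affected share. With 5% of days missing:
- Correlation 0.5, 10% deaths: 0.008/0.150 = +0.05, against −0.017/0.150 = −0.11 without imputation.
- Correlation 0.8, 6% deaths: 0.011/0.154 = +0.07, against −0.010/0.154 = −0.06.
- Correlation 0.8, 11% deaths: 0.015/0.149 = +0.10, against −0.009/0.149 = −0.06.

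**3. Two other simulations, asinh error per imputed patient.** Simulation A (150 per arm, 10% of in-hospital days missing, about 25% of patients imputed): −0.07 without imputation, +0.03 to +0.05 with the planned models, 0.00 with predictive mean matching fitted without deceased patients. Simulation C, which separates the two parts of the remedy: about −0.07 without imputation, +0.07 to +0.08 as planned, about +0.04 with survivors only, about +0.01 with matching on survivors.

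**4. Arm difference.** The standard error is SD × √(2/150) = 0.70 × 0.1155 = 0.081, or 0.087 with SD 0.75.
- Simulation A, 8% versus 3% deaths: shift −0.0049 (Monte Carlo SE 0.0006); 0.0049/0.087 = 0.06 SE. With 5% deaths in both arms: −0.0005.
- Simulation C, unequal deaths: 0.003 to 0.009, or 0.04 to 0.11 SE.
- Simulation B, the extreme of 11% versus no deaths at correlation 0.8 with 5% of days missing: 0.015 − 0.006 = 0.009, or 0.11 SE. Taking 0.012 as an upper limit: 0.012/0.081 = 0.15 SE.

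**The case against.** **The premise is inferred.** Section 17.2.4 does not say that the models run on raw scores or that the 24s are in the data. Section 9 introduces its rules as holding in certain settings without listing them. The code in Addendum 1 assigns 24 and then, further down, sets SOFA to missing on any day without a lab-analysis entry; if no such entry exists after death, the printed code would delete the 24s. This stands: a reader might infer that the SAP prescribes a wrong model, but it only leaves open a detail whose natural reading has this effect. That reading is still the likelier one, since the models are specified for the daily scores, the transformation is tied to the t-test, and nobody is excluded.

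**Imputing as planned is usually better than not imputing.** This also stands. In simulation A the overshoot is 0.03/0.07 = 43% to 0.05/0.07 = 71% of the underestimate. In simulation B the planned method is usually the less biased of the two; the clear exception is correlation 0.8 with 10–11% deaths (+0.53 to +0.59 against −0.30 to −0.34 points). The results do not support a general statement that imputation makes matters worse.

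**Skewness on the raw scale might be thought the main cause.** In raw points it is not: with the models on the asinh scale, simulation B still gives +0.12 to +0.59, whereas leaving out deceased patients removes most of the error. On the asinh scale a smaller error remains among survivors (about +0.04 in simulation C), which matching removes.

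**Few patients are affected.** Also true. Discharged patients keep their observed maximum, section 9 resolves many missing lab values beforehand, and the imputation is worded conditionally. Simulation A's 10% of days missing lies above the 8.1% that section 6 plans for dropout and mortality together; simulation B's 2–5% is the more plausible range.

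**Conclusion.** The point holds as a minor one. If the 24s enter the arm-specific linear models, imputed maxima of survivors are biased upward, and more so where more patients die. Per imputed patient, the overshoot ranges from clearly smaller than to about as large as the underestimate it is meant to correct; it is larger only at the extreme of the settings examined.

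A reader might infer that the treatment comparison is materially biased. The figures do not support that: the shift is near zero with equal deaths and at most about 0.15 SE with unequal deaths. Expressed as a share, 0.0049/0.034 = 14% of the true difference in simulation A looks large only because that true difference is itself under half a standard error. The endpoint is secondary, and section 13 calls these analyses exploratory.

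All sizes depend on assumed early death rates (0 to about 12%), administratively missing days (2–10%) and between-day correlation. This is a free improvement, not an error that endangers a conclusion.

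**What to change.** In 17.2.4:
- Fit the imputation models, still by arm and with 20 data sets, only on patients alive through day 5.
- Set the maximum of patients who died by day 5 to 24 afterwards. Nothing is lost for them, since their maximum is 24 whatever their other days show. The step also secures the section 9 rule regardless of the order of the code lines in Addendum 1.
- Preferably replace the normal draws by predictive mean matching, so that imputed values stay integers within the observed 0–24 range. If linear draws are kept, state their scale and bounds.

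The cost is one data filter, one option in the imputation code and one sentence in the SAP. There is no real downside, and the gain is small if few days are missing.
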